8.3 Potential Benefits of Proposed Research to Subjects and Others (from consent)

There are no assured benefits, but there are several potential benefits from participating in this project. Veteran participants who complete the moral elevation intervention may experience decreased PTSD symptoms, moral injury distress, and improved social functioning. It is also possible that Veteran participants may benefit from increased monitoring that is beyond the standard of care. For example, if a participant discloses suicidality during an assessment, s/he may benefit from clinical referrals. Additionally, there is potential for other Veterans diagnosed with PTSD and/or experiencing moral injury distress to benefit from the findings of this project. Specifically, findings from the proposed project will inform efforts to improve treatment of trauma distress and potentially lead to advances in the amelioration of PTSD and moral injury distress and the facilitation of psychosocial growth and functional recovery.

8.4 Compensation

Veteran participants will each be compensated \$30 for completing the baseline (pre-intervention) assessment and \$15 for completing session measures for each online session (total of 8 online sessions; \$120 for all sessions). Veteran participants in the elevation intervention condition will receive \$40 for completing the 1-week follow-up (post-intervention) assessment and qualitative interview, whereas Veteran participants in the no-treatment condition will each be compensated \$30 for completing the follow-up assessment (no qualitative interview). Thus, the maximum compensation for completing assessments is \$190 for Veterans in the intervention condition and \$180 for Veterans in the no-treatment condition. Significant Other participants, designated by Veteran participants, will be compensated up to \$40 for completing the observer assessments based on the following schedule: \$20 for the baseline assessment and \$20 for the 1-month follow-up assessment. Participants can choose between three payment options: 1) gift cards mailed to their physical address, 2) direct deposit payments after they complete and submit a direct deposit form, and 3) cash vouchers that can be submitted in-person for cash payments at the Waco, Temple, or Austin VA clinics. Participants will be paid according to their preferred method.

Additionally, previous CoE studies have found that reimbursing travel costs significantly contributes to recruitment and retention. For Veterans who choose the cash voucher option, they will be required to travel to the Center of Excellence to pick up the voucher in -person. Therefore, Veteran participants who travel >20 miles each direction between his/her home address and the Center of Excellence to pick up the voucher will be reimbursed for travel; calculated based on the shortest calculated distance x 2 x standard VA rate of 0.415 per mile.

9. Adverse events

An Adverse Event (AE) is any untoward physical or psychological occurrence in a human subject participating in research. These incidents will be reported to the IRB on annual review.

Expected AEs that are more severe than that described in the informed consent documents will be reported to the IRB on annual review.

Unexpected AEs (UAEs) that meet criteria for Unanticipated Problems Involving Risks (UPIR) will be reported to the IRB within 5 business days. Unanticipated and unexpected refer to an event or problem in human research that is new or greater than previously known in terms of nature, severity, or frequency, given the procedures described in protocol documents and the characteristics of the study population.

A Serious Adverse Event (SAE) is an untoward occurrence in human research that results in death, a life-threatening experience, inpatient hospitalization, prolongation of hospitalization, persistent or significant disability or incapacity, congenital anomaly, or birth defect, or that requires medical, surgical, behavioral, social, or other intervention to prevent such an outcome. SAEs will be reported to the IRB within 5 business days after discovery of a SAE that is both unanticipated and related to the research.

Local Research Deaths will be reported by oral notification to the Institutional Review Board (IRB) immediately upon becoming aware of any local research death that is both unanticipated and related to the research.

10. Description of Protocol Drugs or Devices:

None.

11. Modification of the Protocol.

Modification to the protocol, consent form and/or questionnaires will be submitted to the CTVHCS IRB for review prior to implementation.

12. Departure from the Protocol.

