8.1 Risks to Subjects (from consent)

A. Human Subjects Involvement and Characteristics:

All contact with participants will be conducted in a manner consistent with both Health Insurance Portability and Accountability Act (HIPAA) and Institutional Review Board (IRB) guidelines to ensure that the utmost care is taken to protect the welfare and interests of human subjects. This study will be conducted within the Central Texas Veterans Health Care System (CTVHCS). Study personnel will be primarily located at the VA VISN 17 Center of Excellence for Research on Returning War Veterans (CoE) in Waco, Texas, where all administrative and data management tasks will occur. All personnel will be thoroughly trained in the conduct of research involving human subjects and will complete all required trainings and research credentialing prior to initiating contact with potential research participants. This study will enroll 48 Operations Enduring Freedom (OEF), Iraqi Freedom (OIF), and New Dawn (OND) Veterans who are enrolled in the CTVHCS. Participants will be randomized to either an elevation intervention condition or a no-treatment condition. Male and female Veterans from all racial/ethnic backgrounds who have experienced a morally injurious event and have a current diagnosis of posttraumatic stress disorder (PTSD) will be considered for study enrollment. This study will also include 1 Significant Other (SO) participant for each Veteran participant, who will complete observational measures of the Veteran's social behavior. The SO participant will be chosen by the Veteran participant; therefore, it is possible that the SO may not be a Veteran. For this study, assessing the feasibility of including a potentially non-Veteran observer who has frequent contact with the Veteran participant is important because their observational data could assist in more comprehensively capturing the impact of a moral elevation intervention on a Veteran's social functioning in future randomized controlled trials. Further, observational data will inform how participation in the intervention changes the way a Veteran is being perceived by those around him/her, which directly impacts a Veteran's ability to reintegrate into civilian life

B. Sources of Materials:

Data for this project will be obtained specifically for research purposes. Six sources of data will be included in this project:

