Every effort will be made to keep information both private and confidential. Study records may only be disclosed in accordance with federal law, including the Federal Privacy Act, 5 U.S.C.552a, and its implementing regulations. Records may be reviewed by the U.S. Food & Drug Administration (FDA), other U.S. government agencies, Institutional Review Boards including the Central Texas Veterans Health Care System Institutional Review Board and by staff at these institutions that deal with research as part of their official duties. As a result, they may see participant names; however, they are also bound by rules of confidentiality.

All study staff will complete the privacy and data security trainings required by CTVHCS and will be research credentialed. Data will also be protected as mandated by the VA IRB and HIPAA guidelines. All paper and electronic data will be maintained, stored, and destroyed in accordance with VA regulations and the Records Control Schedule (RCS-10-1) approved by the Archivist of the United States. Additionally, in accordance with VA Handbook 6500.2

(Management of Breaches Involving Sensitive Personal Information), incidents (i.e., theft or loss of data or storage media), unauthorized access of sensitive data or storage devices, or non-compliance with security controls will be reported immediately to the VA Police and Security Service (Information Security Officer [ISO] and Privacy Officer [PO]).

B.2 Emotional Distress: Emotional distress or discomfort due to the nature of the assessment questions is expected to be minor and transient. Licensed psychologists will be available at all times in the event that a participant experiences significant emotional distress. In addition, appropriate treatment referrals will be made for study participants when necessary, and participants will be informed of resources available to them.

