If the Veteran participant shares information regarding suicidal ideation at any point during the study (including during telephone screening), the PI or, should the PI be unavailable, a designated licensed psychologist on the study team will be notified immediately, and safety issues will be formally assessed by the PI or designated licensed psychologist using a structured suicide risk assessment interview (adapted from VA's standard CPRS template for suicide risk assessment). If imminently suicidal, the participant will be evaluated for hospitalization according to standard CTVHCS procedures. This would involve a planned psychiatric evaluation in the emergency room (ER). If the participant is on VA grounds, they will be escorted to the ER. If they are at home, they will be instructed to come to the ER. If the participant is unwilling to seek care, the police will be called. These procedures have been in place at the study site for other ongoing studies and have been approved by the IRB. All adverse events will immediately be reported to the IRB.

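### Section 9 of the protocol labels adverse events worse than the consent describes as expected, while its next paragraph makes greater-than-known severity unexpected, and no rule says which class governs

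*Protocol*

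**What the plan says.** Section 9 of the protocol sets out its reporting classes in sequence.

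- Adverse events in general: "These incidents will be reported to the IRB on annual review".
- Expected adverse events: those "that are more severe than that described in the informed consent documents will be reported to the IRB on annual review".
- Unexpected adverse events: those "that meet criteria for Unanticipated Problems Involving Risks (UPIR) will be reported to the IRB within 5 business days". The same paragraph defines unanticipated and unexpected as "new or greater than previously known in terms of nature, severity, or frequency, given the procedures described in protocol documents", and adds the characteristics of the study population to that benchmark.
- Serious adverse events go to the IRB within 5 business days, and local research deaths are notified orally at once. In both cases this applies only if the event is unanticipated and related to the research.

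Two other places bear on the point. Section 8.2 B.2 says that emotional distress from the assessment questions "is expected to be minor and transient", and Section 8.1 C.2 describes the same risk in similar terms. Section 8.2 B.2 also ends its paragraph on suicidal ideation with a general statement: "All adverse events will immediately be reported to the IRB".

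The SAP does not deal with adverse events.

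**The concern.** An event of a known type that turns out worse than described seems to belong to two classes at once. The expected-event sentence claims it because it exceeds the consent description. The next paragraph claims it because its severity is greater than was known. Section 9 does not say which reading takes precedence.

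The label matters because every expedited route in Section 9 depends on it. The UPIR route starts from an unexpected event, and the routes for serious adverse events and deaths both require the event to be unanticipated. A staff member who reads the expected-event sentence first, and stops there, could file a markedly worse reaction for annual review. In this trial the foreseeable psychological harm is emotional distress, so distress that is severe or lasting is the event whose class most needs to be clear. Each Veteran takes part for 6 weeks, so an item held for annual review may be read after that Veteran has left the study.

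**Working it through.** No arithmetic applies: the plan states no figure here, and the point depends on none. The check is to set the two sentences side by side and then run test cases through them.

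**Step 1: compare the two classes.**

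| | Expected-event sentence | Unexpected-event paragraph |
|---|---|---|
| Trigger | Severity above the description | New, or above what was known in nature, severity or frequency |
| Benchmark | Informed consent documents | Protocol documents and study population |
| Timing | Annual review | 5 business days, if UPIR criteria are met |
| Precedence over the other class | None stated | None stated |

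The triggers coincide on severity. Only the benchmark can keep the classes apart.

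**Step 2: ask how far the benchmarks differ.** Sections 8.1 and 8.2, which hold the protocol's description of risk, are both headed as taken from the consent. On the protocol's own account, then, its description of severity is the consent's description. The reference to protocol documents therefore does little to separate the classes. The reference to the study population can still separate some events.

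**Step 3: run the cases under Section 9.**

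| Event | Class or classes | Timing |
|---|---|---|
| (a) Distress that is mild and brief, as described | General adverse event only | Annual review; no conflict |
| (b) Distress above the consent description but already known for this population | Expected only | Annual review; no conflict |
| (c) Distress above both benchmarks, UPIR criteria not met, not serious | Both | Annual review under the expected-event sentence. The unexpected-event paragraph sets no deadline, so the general rule of annual review applies; no conflict |
| (d) Distress above both benchmarks, UPIR criteria met | Both | Annual review against 5 business days; conflict |
| (e) A related serious event of a known type, above both benchmarks | Both | 5 business days if treated as unanticipated, annual review if the expected label is allowed to decide; conflict |

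A related death of a known type behaves like case (e), with immediate oral notification in place of 5 business days.

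**Step 4: read the result.** The double classification arises in (c), (d) and (e). The deadlines diverge only in (d) and (e). Section 9 names the UPIR criteria but does not list them, so the documents do not show how often (d) would occur.

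**Step 5: add Section 8.2 B.2.** Read literally, its statement puts every row on immediate reporting, which disagrees with Section 9 even in case (a). That is a separate mismatch. Aligning 8.2 to Section 9 would leave (d) and (e) as they are. Aligning Section 9 to 8.2 would remove the timing difference but leave the classes overlapping.

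**The case against.** The strongest reply is that the benchmarks are different by design. Every Veteran enrolled has screened positive for PTSD and for distress over a morally injurious event (Section 6.3). Marked distress might exceed a consent description of minor distress and still be known for such a population. That is case (b), and it stands: a reader might infer that an expected event more severe than described is a contradiction in terms, and the documents do not show that. What they show is an overlap with no precedence rule, because Section 9 never draws the distinction that this reply needs.

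A second reply is that the expected-event sentence exempts nothing. An event that meets the definition of unexpected and the UPIR criteria is due in 5 business days whatever else is said about it. This is also fair. A reader might infer that a mislabelled event is shut out of the UPIR assessment altogether, but the text does not say so. The risk is that staff apply the first matching label, which is a matter of practice that the wording invites but does not require.

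Third, other safeguards exist. Section 8.2 B.2 calls for immediate reporting of adverse events, and suicidal ideation prompts immediate notification of the principal investigator or a designated psychologist. These reduce the practical harm. They do not settle which Section 9 class applies, and the first of them is itself in conflict with Section 9.

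Finally, the consent text is not among the documents reviewed, so its description of distress is known only through the protocol sections said to be drawn from it.

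**Conclusion.** The point holds as a flaw of classification in Section 9. A known type of event that is worse than described can be both expected and unexpected, and nothing says which governs. The consequence for timing is confined to events that meet the UPIR criteria and to unanticipated, related serious adverse events, including deaths. For these, an expected label could move the report from 5 business days (or immediate notification, for a death) to the annual review.

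This rests on two assumptions: that the protocol's risk sections reflect the consent, as their headings say, and that Section 9 rather than Section 8.2 B.2 is the rule followed. If the immediate-reporting statement in 8.2 prevails, the delay disappears and only the overlapping labels remain.

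A reader might also infer that a delayed report would expose a countable number of further Veterans. The documents do not support such a count. They give no date for annual review, they do not say that a report to the IRB would pause recruitment, and any figure would have to ignore Section 8.2 B.2.

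The matter is worth correcting because it concerns safety reporting and the remedy is small. It does not touch the sample size, the endpoints or the analysis.

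**What to change.** Remove the sentence on expected adverse events that exceed the consent description, or reword it. The replacement should say that any adverse event going beyond what was already known of its nature, severity or frequency is first assessed as unexpected and against the UPIR criteria, and only then assigned to annual review if it does not qualify for a faster route. The benchmark should be the one Section 9 already uses in its definition, namely the protocol documents and the study population, not the consent documents. If the sponsor wants to keep a consent-based class for cases such as (b), the sentence should say that the definition of unexpected governs wherever the two meet.

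In the same edit, reconcile Section 9 with the immediate-reporting statement in Section 8.2 B.2. Which timetable should prevail is for the sponsor and the IRB; this point does not presume the answer.

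The cost is one sentence removed or reworded in Section 9, a matching change in whichever of the two sections gives way, IRB review of the modification before it is implemented (Section 11), and perhaps a few more events assessed against the UPIR criteria.

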12.1 Minor departures from protocol

Minor or administrative protocol deviations are defined as those which do not affect the scientific soundness of the research plan or the rights, safety, or welfare of human subjects. Minor deviations do not result in or require any substantive action to be taken or result in any change to the subject's condition or status (i.e., did not affect the subject's participation in any way, did not result in a change to the subject's emotional or clinical condition, did not cause an adverse experience or require a change to the clinical care of the subject, etc.).

12.2 Departures from protocol

Protocol deviations are defined as those which affect the scientific soundness of the research plan or the rights, safety, or welfare of human subjects. These will require substantive action because the event affects the subject's participation, results in a change to the subject's emotional or clinical condition or requires a change to the clinical care of the subject. An example of a protocol deviation would be an administrative error resulting in a missing page on the informed consent document that was signed by the subject, indicating the subject may not have been fully informed about the protocol before signing the document. Another example would be a fire alarm intrusion into testing session that resulting in a truncated testing session, and resulting in a change in the subject's emotional state due to fear of bodily harm. We will report protocol deviations to the local IRB for review and approval within 5 days of becoming aware of the deviation.

13. References

- 2. Van Vliet KJ. Shame and avoidance in trauma. In: Martz E, editor. Trauma rehabilitation after war and conflict. New York (NY): Springer; 2010.
- 3. Finlay LD. Evidence-based trauma treatment: problems with a cognitive reappraisal of guilt. J Theor Philos Psychol. 2015;35(4):220-9.
- 8. Cox KS. Elevation predicts domain-specific volunteerism 3 months later. J Posit Psychol. 2010;5(5):333-41.

**Title: Pilot Study Testing a Web-Based Moral Elevation Intervention for
Veterans with PTSD and Moral Injury**

ID: D3035-P

NCT: NCT03906240

Principal Investigator: [name].

Statistical Analysis Plan

Date: 06.22.2021

Statistical Analysis Plan

All data management and analyses were conducted with R (R Core Team, 2021). To assess the feasibility and acceptability of MOVED, we calculated descriptive statistics for recruitment and retention data, self-report measures that focused on evaluating components of the intervention, and state elevation scores. For all evaluation measures, the mid-point score for a given measure was used as an indicator for adequate feasibility and acceptability (e.g., average/medium levels of acceptability, or higher). The mid-point score for state elevation was also used as an indicator for feasibility to induce elevation.

Qualitative interviews were transcribed, then coded using an inductive approach by two members of the research team and the first author. Two coders reviewed all transcriptions independently, identified codes based on interview responses, then met to discuss and modify codes. A consensus codebook was established and re-applied to all transcriptions. Emergent themes and subthemes were identified by the first author.

Preliminary examination of outcome measures was conducted via paired samples *t*-tests with the base stats package (`t.test`) and Cohen's *d* effect sizes within each condition with the `rstatix` package (Kassambara, 2021). Assessment of changes in pre-post measures included all participants who were randomized and provided post-session data.

References

- R Core Team. R: A language and environment for statistical computing. R Foundation for Statistical Computing [Internet]. 2021. Available from: <https://www.R-project.org/>
- Kassambara, A. `rstatix`: Pipe-Friendly Framework for Basic Statistical Tests [Internet]. 2021. Available from: <https://cran.r-project.org/web/packages/rstatix>
